Appendix

Appendix A: Study administrative structure

Appendix B: Investigator agreement

1. Background

Bipolar disorder is a mood disorder with symptoms of excessive fluctuations in mood, emotion, and drive, and typically characterized by repeated occurrence of manic or hypomanic episodes and major depressive episodes. The core symptoms of manic or hypomanic episodes include abnormally elevated, expansive or irritable mood, and those of major depressive episodes include depressed mood and loss of interest or pleasure. According to the Diagnostic and Statistical Manual of Mental Disorders, fourth edition, Text Revision (DSM-IV-TR), bipolar disorder can be classified broadly into two types: bipolar I and II disorder. Bipolar I disorder involves manic episodes and major depressive episodes, while bipolar II disorder involves hypomanic episodes and major depressive episodes. The lifetime prevalence of bipolar I disorder varies from 0.2% to 2.0% ¹⁾ in various countries, and is reported to be 0.5% ²⁾ in Japan.

In the DSM-IV-TR, bipolar depressive state is defined as “the current (or most recent) major depressive episode with a history of at least one manic or mixed episode.” An observation study ^{3), 4)} shows that the patients with bipolar I disorder had depressive symptoms for 32% of the followed duration (longer than 10 years) and manic/hypomanic symptoms for 9% of the duration, and that the patients with bipolar II disorder had depressive symptoms for 50% of the duration and manic/hypomanic symptoms for 1% of the duration. The study results indicate that the depressive state was predominant. Since frequent depressive episodes associated with bipolar disorder significantly interfere with social functioning and family life, the depressive state can impair the quality of life (QOL) ^{5), 6)}. In addition, the suicide rate among patients with bipolar I disorder has been reported to be approximately 10% to 15%, and most suicides are committed in the depressive or mixed state ⁷⁾. Given the impact on QOL and high suicide rates, treatment of depressive symptoms associated with bipolar disorder is very important.

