6.3 Safety measurements

6.3.1 Adverse events

6.3.1.1 Definitions

The definitions of adverse events (AEs) and serious adverse events (SAEs) are shown below. It is of the utmost importance that all staff members involved in the study are familiar with the content of this section. The principal investigator will be responsible for ensuring that all site staff have read and understand this content.

Adverse events

An adverse event (AE) is any untoward medical occurrence in a patient treated with a medicinal (investigational) product and which does not necessarily have a causal relationship with this treatment. An AE can, therefore, be any unfavorable and unintended sign (eg, an abnormal laboratory finding), symptom, or disease occurring after the administration of a medicinal (investigational) product, whether or not considered related to the medicinal (investigational) product. AEs may include the onset of new illness and the exacerbation of pre-existing conditions.

Lack of efficacy may be an expected potential outcome and should not be reported as an adverse event unless the event is unusual in some way.

The investigator should attempt to establish a diagnosis of the event based on signs, symptoms, and/or other clinical information. In such cases, the diagnosis should be documented as the AE and not the individual signs/symptoms.

Serious adverse events (SAEs)

A serious adverse event (SAE) is an AE that meets one or more of the following criteria:

- Results in death.
- Is life-threatening (ie, a patient is at immediate risk of death at the time of the event, not an event where occurrence in a more severe form might have caused death).
- Requires hospitalization or prolongation of existing hospitalization.
- Results in persistent or significant disability or incapacity.
- Is a congenital anomaly or birth defect.
- Is an important medical event that may jeopardize the patient or may require a medical or surgical intervention to prevent one of the outcomes listed above. Examples of such medical events include allergic bronchospasm requiring

intensive treatment in an emergency room or at home, blood dyscrasias or convulsions that do not result in inpatient hospitalization.

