17.1.5.3. Mood event-related TEAEs

The overall incidence of mood event-related TEAEs will be summarized by Preferred Term and treatment group. These will be identified by using a list of specified terms from medical personnel, which can be found in Appendix 3. This summary will be repeated for all Japanese subjects up to Week 52 overall, by Mood Stabilizer and by Most Recent or Current Episode subgroups separately as well.

Document: K:\DSP\SM-13496\RVA97109\Biostatistics\Documentation\SAP

Author: [REDACTED]

Version Number:

1.0

Version Date:

20MAR2018

Template No: CS_TP_BS016 – Revision 3

Reference: CS_WI_BS005

Effective Date: 01May2012

Copyright © 2012 [REDACTED] All rights reserved.

The contents of this document are confidential and proprietary to [REDACTED]. Unauthorized use, disclosure or reproduction is strictly prohibited.

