17.2. DEATHS

If any subjects died during the study, the information will be presented in a data listing. Deaths will be recorded on either the AE panel as an AE leading to death ("Fatal" AE), or on the C-SSRS panel as a lethal suicide attempt.

Document:	K:\DSP\SM-13496\RVA97109\Biostatistics\Documentation\SAP		
Author:	[REDACTED]	Version Number:	1.0
		Version Date:	20MAR2018

Template No: CS_TP_BS016 – Revision 3
Effective Date: 01May2012

Reference: CS_WI_BS005

Copyright © 2012 [REDACTED] All rights reserved.

The contents of this document are confidential and proprietary to [REDACTED]. Unauthorized use, disclosure or reproduction is strictly prohibited.

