APPENDIX 3. MEDICAL REVIEW OF TERMS

EPS Terms	Metabolic Terms	Combined Terms	Treatment Emergent Mania Terms	Mood Event Terms
Muscle rigidity	Blood cholesterol increased	Parkinsonism: Muscle rigidity, Bradykinesia, Parkinsonism, Tremor, Psychomotor retardation	Bipolar disorder	Disease progression
Trismus	Blood glucose increased		Euphoric mood	Apathy
Bradykinesia	Blood insulin increased		Hypomania	Bipolar disorder
Dystonia	Blood triglycerides increased		Mania	Depression
Parkinsonism	Fructosamine increased			Euphoric mood
Tremor	Glucose urine present			Hypomania
Psychomotor retardation	High density lipoprotein decreased	Dystonia: Dystonia, Trismus		Intentional self-injury
	Lipids abnormal	Somnolence: Hypersomnia, Sedation, Somnolence		Listless
	Low density lipoprotein increased			Mania
	Weight increased			Self-injurious ideation
	Diabetes mellitus			Suicidal ideation
	Dyslipidaemia			Suicide attempt
	Glucose tolerance impaired			
	Hypercholesterolaemia			
	Hyperglycaemia			
	Hyperinsulinaemia			
	Hyperlipidaemia			
	Hypertriglyceridaemia			
	Metabolic disorder			

Document: K:\DSP\SM-13496\RVA97109\Biostatistics\Documentation\SAP
 Author: [Redacted] Version Number: 1.0
 Version Date: 20MAR2018

Template No: CS_TP_BS016 – Revision 3 Reference: CS_WI_BS005
 Effective Date: 01May2012

Copyright © 2012 [Redacted] All rights reserved.
 The contents of this document are confidential and proprietary to [Redacted]. Unauthorized use, disclosure or reproduction is strictly prohibited.

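### The Appendix 3 list that defines mood event-related TEAEs omits completed suicide and depressed mood, so one descriptive safety summary can undercount (minor)

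*SAP*

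**What the plan says.** SAP 17.1.5.3 sets up a special-interest summary: "The overall incidence of mood event-related TEAEs will be summarized by Preferred Term and treatment group". It gives one rule for membership: "These will be identified by using a list of specified terms from medical personnel, which can be found in Appendix 3". The summary is repeated for Japanese subjects up to Week 52, overall, by mood stabilizer and by most recent or current episode.

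The Mood Event Terms column of Appendix 3 has 12 entries: disease progression, apathy, bipolar disorder, depression, euphoric mood, hypomania, intentional self-injury, listless, mania, self-injurious ideation, suicidal ideation and "Suicide attempt".

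Three other passages bear on the list:
- Protocol section 1 (Background) describes the core symptoms of manic or hypomanic episodes and says that "those of major depressive episodes include depressed mood and loss of interest or pleasure".
- SAP 17.2 foresees a suicide death. It may be recorded as a fatal AE "or on the C-SSRS panel as a lethal suicide attempt".
- Protocol 6.3.1.1 says that, when a diagnosis can be made, "the diagnosis should be documented as the AE and not the individual signs/symptoms".

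**The concern.** The list follows suicidality from ideation through self-injury to attempt and stops before the fatal outcome. It also works partly at symptom level (euphoric mood, apathy, listless), yet leaves out depressed mood, which the protocol itself treats as a core depressive symptom. Membership is decided by the list alone, so an event under either missing term is not a mood event for this table, however clearly it is one clinically.

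What is at stake is the completeness of the one special-interest AE summary that the SAP defines for mood events. A reader would expect a table that counts suicide attempts to count a suicide as well.

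**Working it through.** **1. List check.** Each term is set against the 12 entries in Appendix 3.

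| Term | On the list? |
|---|---|
| Suicidal ideation | Yes |
| Suicide attempt | Yes |
| Euphoric mood | Yes |
| Apathy | Yes |
| Depression | Yes |
| Completed suicide | No |
| Depressed mood | No |
| Irritability | No |

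After its first entry the column runs in alphabetical order from apathy to suicide attempt with no visible break, so a loss in text extraction is unlikely.

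**2. Is there a rule that brings the missing terms back?** Neither SAP 17.1.5.3 nor Appendix 3 has a related-terms provision. SAP 17.1 extends the TEAE window to 14 days after the last dose for serious events and deaths (7 days otherwise). A suicide in that window, entered as an AE, can thus be a TEAE without being a mood event-related TEAE.

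**3. Where would a suicide be reported otherwise?**
- If entered as an AE: the all-TEAE tables (SAP 17.1.1), the serious TEAE summary and listing (17.1.3), the fatal TEAE listing (17.1.4) and the deaths listing (17.2).
- If captured on the C-SSRS: the deaths listing (17.2) and the suicidal behavior and suicidality summaries (17.7.2, 17.7.2.1). SAP 17.7.2 counts any attempt as suicidal behavior and rates lethality up to death. SAP 17.7.2.2 repeats the overall C-SSRS summary for Japan by mood stabilizer and most recent or current episode, the same subgroups as the mood-event table.

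**4. Size per uncounted subject.** Protocol 3.5 and SAP 3.2 give targets of 325 prior-study completers and 80 new recruits.
- All subjects: N = 325 + 80 = 405, and 1/405 = 0.0025, or 0.25 percentage points.
- New recruits: 1/80 = 0.0125, or 1.25 percentage points.

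These figures assume that everyone in the target is treated and so enters the safety population. The plan states no expected mood-event incidence, so there is no figure of its own to reproduce and no total understatement to compute.

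**The case against.** The strongest case on the other side has four parts.

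- **Nothing is lost from reporting.** A suicide appears in several other outputs, some by the same subgroups. This stands, and it limits the point to one table and its repeats. A reader might infer that the plan hides suicides; it does not.
- **Recording rules narrow the symptom gap.** Sites are to record diagnoses in preference to symptoms, so much depressed mood would enter as depression or bipolar disorder, both listed. Protocol 6.3.1.1 also keeps ordinary lack of efficacy out of the AE record. This stands in part. The diagnosis rule works only where a diagnosis is made, and the list's own symptom-level entries show that some symptoms were meant to count.
- **The list may hold only terms already seen in the study**, in which case nothing is missed. SAP 17.1.7.3 says that its combined terms come from review of coded AEs, but the SAP does not say so for the mood-event list. This remains possible but unstated.
- **A lethal attempt might be coded to the listed attempt term.** The SAP does not say, so this also stays open.

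A reader might further infer that the list is biased towards the manic pole, because elevated mood counts and depressed mood does not. The documents do not support that. Depression, apathy and listless are listed on the depressive side. Irritable mood, which protocol section 1 names as a core manic symptom, is absent on the manic side. No direction of imbalance follows.

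A reader might also suspect gaps for mixed episodes or bipolar I disorder. Those turn on how the coding dictionary arranges its terms, which cannot be checked from these documents.

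**Conclusion.** The point holds as a minor gap in the counting rule. As written, a subject whose only mood TEAE is coded to completed suicide or depressed mood is left out of the mood event-related incidence. The omission can only lower that incidence: by 0.25 percentage points per subject overall, and by 1.25 points per subject among new recruits, at target enrolment. How many subjects are affected is unknown and could be zero. It is tempting to assume a rate for depressed mood and multiply it out, but the documents give no basis for any such rate.

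The conclusion assumes that terms are matched to the list exactly as printed, and that a suicide is not coded under the attempt term. No endpoint, comparison or other safety output changes. The study is open-label, has no hypotheses, and presents this table descriptively. Irritability is a less specific term, and whether it belongs is a medical judgement, so its absence is a query and not an established omission.

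**What to change.** - Add completed suicide and depressed mood to the Mood Event Terms column of Appendix 3.
- Have the medical personnel responsible for the list recheck it against all coded AE terms before database lock, including a decision on irritability, and state in the SAP how the list was built.
- Reconcile any lethal attempt on the C-SSRS panel with the AE panel so that a matching AE exists. Inserting a C-SSRS-only death directly into this table would not work, because the table is organized by preferred term and such a record has none.

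The cost is a short list edit, one medical review and one data reconciliation, with no new data collection. The only downside is that the reported incidence may be slightly higher.
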